### **6.2.2 Preparation and Administration**

Investigational study medication will be prepared and dispensed by properly trained and delegated individuals. Patients will self-administer itacitinib by mouth regardless of food once daily. Doses should be taken every morning ( $\pm$  8 hours) and recorded on the patient's dosing diary. Patients should be instructed to hold their dose until after their blood is drawn on days that they will be seen in the clinic. Doses missed outside of the dosing window should not be made up, but rather, patients should be instructed to take their next dose at their regularly scheduled time.

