ANC < 0.5 × 10  /L, suspected as unrelated to study drug (e.g., GVHD, active cytomegalovirus viremia).	
 
● Reduce dose by 1 dose level.
 
● Monitor ANC count as clinically indicated.
 
● Resume the previous dose if the ANC count is ≥ 0.5 × 10^9/L for more than 7 days.
 

ANC < 0.5 × 10  /L, suspected as related to study drug.	
 
● Interrupt for up to 14 days.
 
● Monitor ANC count as clinically indicated.
 
● Resume at a reduced dose if the ANC count is ≥ 0.5 × 10^9/L for more than 7 days. If the ANC count remains at ≥ 0.5 × 10^9/L for more than 7 days after resuming treatment at a lower dose, the previous dose may be resumed.
 

Thrombocytopenia	
Platelet count < 10 × 10  /L or platelet count has decreased by ≥ 50% from baseline, suspected as unrelated to study drug.	
 
● Reduce dose by 1 dose level.
 
● Monitor platelet count as clinically indicated.
 

ADVERSE EVENT	MANAGEMENT
	
 
Resume at previous dose if platelet count returns to <math>\geq 20 \times 10^9/L</math> or recovers to within 75% of the baseline value for more than 7 days.
 

Platelet count $< 10 \times 10^9/L$ or platelet count has decreased by $\geq 50\%$ from baseline, suspected as related to study drug.	
 
Interrupt for up to 14 days.
 
Monitor platelet count as clinically indicated.
 
Resume at a reduced dose if platelet count returns to <math>\geq 20 \times 10^9/L</math> for more than 7 days or recovers to within 75% of the baseline value. If the platelet count remains stable for an additional 7 days, the previous dose may be resumed.
 

Other Non-hematologic toxicities	
Any Grade 1 or Grade 2 toxicity.	
 
Continue treatment and manage the toxicity.
 
Monitor as clinically indicated.
 

Any Grade 3 toxicity, not manageable by supportive care.	
 
Interrupt up to 14 days until toxicity resolves to <math>\leq</math> Grade 1.
 
Restart at the same dose; if assessed as related to itacitinib, restart at next lower dose and monitor as clinically indicated.
 

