Itacitinib has the potential to cause WBC margination (i.e., a transient decrease in absolute neutrophil count [ANC]), assessment of hematology parameters should be performed before study drug administration at all applicable study visits.

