 Monitoring for infection will be performed at screening and for the duration of study therapy per institutional practice. Testing for cytomegalovirus and Epstein-Barr virus will be performed at screening. Prior test results obtained as part of standard of care before allo-HCT may be used for purposes of eligibility and tests do not need to be repeated. Routine infection monitoring should occur during the study as per institutional practice and include at a minimum PCR

testing on plasma for CMV and EBV and monitoring for fungal infections (i.e. Aspergillus). Additional monitoring should be performed during treatment if there is clinical suspicion of an infection.

 Screening assessment may be used if completed within 7 days prior to C1D1.

 Graft failure/chimerism should be performed on whole blood and should include: Chimerism, Post-Transplant and Chimerism, Post-Cell Sort, T cells.

 Participants will be closely monitored for any evidence of underlying disease relapse or recurrence during study therapy. These evaluations will be conducted in accordance with local institutional practices.

 To be completed prior to the physical exam at C1D1, C2D1, C3D1, C6D1, C8D1, C10D1, and EOT or PD visit.

 ECP will be given at a frequency of twice weekly for 8 weeks followed by a standard taper schedule as per study protocol. Refer to Table 4 for taper schedule.

 All patients will undergo 5 to 10 days of itacitinib monotherapy. The first ECP treatment will be considered C1D1. On days that the patient is being seen in clinic, itacitinib dosing does not need to be held prior to routine blood draws or for correlative studies.

 Patients may be on immune suppression at the time of study enrollment. On days that the patient is being seen in clinic, immunosuppressives should be held until after the blood draws if trying to achieve a therapeutic level. See Section 6.1.3.

 Correlative studies are only required during dose expansion. On days of drug administration, correlative blood samples should be drawn without regard to itacitinib dosing or ECP therapy. Patients should take itacitinib at their usual time. Blood will be drawn at screening, C1D1, the time of response, C7D1, and at EOT or progression, whichever occurs first.

 Only to be drawn from the first nine patients enrolled in Part 2, Dose Expansion.

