### 10.4 Laboratory Assessments

Samples for all laboratory assessments will be drawn at the time points indicated in the Schedule of Events and when clinically indicated. Laboratory tests may be performed up to 3 days prior to the scheduled clinic visit. All safety laboratory analyses will be performed by the local laboratory for each study center. All safety laboratory assessments must be reviewed by the treating investigator prior to study drug administration. When applicable, results from the pregnancy test must also be available for review prior to dosing.

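### Footnote 26 of the Schedule of Events permits itacitinib before routine blood draws, contrary to Section 6.2.2, and so allows the post-dose ANC values that Section 7.5 is written to avoid

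*Combined protocol and SAP*

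**What the plan says.** Four places in the current protocol govern when itacitinib is taken relative to a blood draw.

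- **Table 7, footnote 26:** on days the patient is seen in clinic, "itacitinib dosing does not need to be held prior to routine blood draws or for correlative studies".
- **Section 6.2.2:** "Patients should be instructed to hold their dose until after their blood is drawn on days that they will be seen in the clinic". The same section sets the usual dosing time: "Doses should be taken every morning", with a window of ± 8 hours.
- **Section 7.5:** "Itacitinib has the potential to cause WBC margination", explained there as a transient fall in ANC. For that reason "assessment of hematology parameters should be performed before study drug administration at all applicable study visits".
- **Section 10.4:** "All safety laboratory assessments must be reviewed by the treating investigator prior to study drug administration". It also says "Laboratory tests may be performed up to 3 days prior to the scheduled clinic visit".

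Footnote 28 adds that correlative samples are drawn without regard to dosing and that patients take the drug at their usual time. None of these texts refers to another or says which prevails.

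Table 6 is where an ANC result has consequences. For ANC < 0.5 × 10^9/L judged related to study drug, itacitinib is interrupted for up to 14 days. Then: "Resume at a reduced dose if the ANC count is" at or above 0.5 × 10^9/L for more than 7 days. If judged unrelated, the dose is reduced by one level.

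**The concern.** Section 7.5 gives a pharmacological reason for pre-dose hematology: a post-dose sample may show a temporary dip that does not reflect marrow function. Footnote 26 allows exactly that sample, in the table that site staff use to run visits. Section 8 says the schedule will be followed throughout the study, whereas the rationale for pre-dose sampling is the last paragraph of a supportive-care section.

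At stake is dosing in individual patients. A margination dip is a drug effect, so the related branch of Table 6 is the natural one to apply. One reading below 0.5 × 10^9/L could then lead to an interruption and a restart at a lower dose. From 200 mg daily, one level down is 100 mg daily, half the dose.

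**Working it through.** The plan states no figure to reproduce. The check compares the texts and then bounds the exposure.

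**1. Does footnote 26 reach the ANC draw?** Footnote 12 defines hematology as a CBC with differential and platelets, and Table 7 schedules it at every on-treatment visit. It is therefore a routine draw.

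**2. Which site behaviour complies with what?**

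| Behaviour on a clinic day | Footnote 26 | Section 6.2.2 | Section 7.5 |
|---|---|---|---|
| Hold dose until after the draw | complies | complies | complies |
| Dose first, then draw | complies | breaches | departs from it |

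The footnote is a permission that is too broad.

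**3. Does the 3-day laboratory allowance in Section 10.4 cure it?** No. Dosing is daily at 200 mg and 100 mg, so a sample taken on an earlier day can also be post-dose. The tension with review of results before dosing is only implied, and arises only when labs are drawn on the day of the visit.

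**4. Scheduled draws exposed.** Table 7, Day 1 hematology after the dose-limiting toxicity (DLT) period:
- Cycles 2–3: 2
- Cycles 4–7: 4
- Cycles 8–12: 5
- Total: 2 + 4 + 5 = 11. By the Cycle 7 Day 1 (24-week) visit: 2 + 4 = 6.

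Cycle 1 Days 1 and 15 are left out because Sections 7.1 and 7.4 keep Table 6 reductions out of the DLT period. Section 6.1 limits treatment beyond six cycles to patients with PR or better (Sections 6.7 and 9.2 are less restrictive), so many patients will not reach the last five draws.

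**5. Fall needed to reach the Table 6 threshold.** For pre-dose ANC *A* (× 10^9/L), the fall that just reaches 0.5 is (*A* − 0.5)/*A*, and the fall must exceed this. The entry floor in Section 5.1.9 is 1000/mcL = 1.0 × 10^9/L. The other values of *A* are assumptions.

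| Pre-dose ANC | Calculation | Fall must exceed |
|---|---|---|
| 0.6 (assumed) | 0.1/0.6 | 16.7% |
| 0.8 (assumed) | 0.3/0.8 | 37.5% |
| 1.0 (entry floor) | 0.5/1.0 | 50% |
| 2.0 (assumed) | 1.5/2.0 | 75% |

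**6. Is a reduction reversible?** Table 6 allows the previous dose to be resumed once the count has held. Section 7.3 says a reduced dose stays for all later cycles and bars re-escalation within a patient. A site following Section 7.3 could make the reduction permanent.

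**7. Footnote 28.** Every scheduled correlative column in Table 7 (screening, Cycle 1 Day 1, Cycle 7 Day 1, progression, end of treatment) also has hematology. If a patient's usual morning dose precedes the Cycle 7 Day 1 visit, the usual-time instruction and the Section 6.2.2 hold cannot both be met.

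**The case against.** The strongest reply is that harm needs a chain of events. A site must prefer a footnote to two body sections. The dip must cross 0.5 × 10^9/L. The investigator must miss that it is transient, and must then act on one value. Section 7.4 makes Table 6 guidance, asks for clinical judgment, and says transient (≤ 72 hours) asymptomatic laboratory values may be exempted. Section 16.4 treats a laboratory value as an adverse event only if it causes signs or symptoms, is clinically significant or needs therapy. Section 8 also describes the schedule as an overview.

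Most of this stands and limits the point. It does not remove it. The Section 7.4 exemption is optional and depends on recognising the value as transient. The next scheduled Day 1 draw is a 28-day cycle later, so an extra test would be needed to show it.

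Three stronger readings are tempting but unsupported:

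- *A site cannot follow both instructions.* For routine draws it can, by holding the dose, because footnote 26 permits earlier dosing without directing it. Section 7.5 also says pre-dose hematology should be done, which is short of a strict requirement.
- *DLT counts are distorted.* The neutrophil-count items in Table 3 need Grade 4 neutropenia lasting more than 7 days, or failing to recover to Grade 2 or better within 7 days of interruption. One transient value meets neither. The general item on reactions leading to dose reduction is not a ready route, since Section 7.1 bars reductions in the DLT period unless a DLT is already confirmed.
- *The primary analysis is affected.* The documents give no basis for sizing any change in response rate.

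**Conclusion.** The point holds as a contradiction between an operating instruction and the body of the protocol, and it should be corrected. The textual conflict is certain. Its clinical effect is possible but cannot be estimated, because the documents give neither the size nor the frequency of the ANC dip. The 11 draws are an upper limit on scheduled opportunities in a patient who completes 12 cycles and doses before every draw; they are not an expected number of events. The threshold calculation places the risk mainly in patients whose ANC is already low. Section 7.4 reduces the chance of an unneeded dose change, while the disagreement between Table 6 and Section 7.3 could make one last. No effect on the primary endpoint, type I error or power is claimed.

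**What to change.** In footnote 26, remove routine draws from the permission, leaving it for correlative samples only, and add: *On any day hematology or safety labs are drawn, itacitinib is held until after that draw (Sections 6.2.2 and 7.5).*

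In footnote 28, keep the rule that correlative samples are drawn without regard to dosing. Replace the usual-time sentence with: *Itacitinib is taken after the hematology draw when one is due that day, and at the usual time otherwise.*

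The cost is wording in two footnotes and a short dose delay on draw days, which should usually fit the ± 8 hour window. No visit or sample is added. There is one small downside. Because hematology is due on every scheduled on-treatment correlative day, the dose will be delayed on those days, and correlative samples taken in the same draw will be pre-dose. The JAK1/STAT phosphorylation endpoint in Section 1.3.2 may depend on time since dose. The time of the last dose, which Section 6.2.3 already has patients enter in the dosing diary, should therefore be recorded for the pharmacodynamic analysis.

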## **9 STUDY PROCEDURES**

### **9.1 Screening Evaluations**

For screening procedures see the Schedule of Events and the Assessments Section. Screening activities may only begin after a subject has signed consent. All screening activities must take place within 28 days prior to Cycle 1 Day 1 unless otherwise noted.

### **9.2 Treatment Period**

Once a subject has completed screening, has been found to be eligible, and has been registered, treatment procedures may begin. In the absence of disease progression or toxicity, patients may continue to undergo 12 cycles of itacitinib therapy. See the Schedule of Events and the Assessments Section for treatment period procedures.

### **9.3 Disease progression**

Upon disease progression, study therapy will be discontinued. Procedures required at the time of disease progression are noted in the Schedule of Events and should occur at the time of identified disease progression. Patients who do not experience disease progression while on study therapy will be followed for GVHD progression for 6 months after the end of treatment visit. If disease progression occurs during follow-up, the assessments and procedures listed on the Schedule of Events will be conducted at the time of progression.

### **9.4 End of Treatment**

End of treatment evaluations will occur 30 days after the last treatment dose of itacitinib. For End of Treatment procedures see the Schedule of Events and the Assessments Section.

### **9.5 Follow-up Evaluations**

All patients will be followed for a total of 12 months every 12 weeks ( $\pm 7$  days) after removal from study treatment for GVHD progression, initiation of alternative therapy for GVHD, relapse of the underlying disease, or death. Patients removed from the study for unacceptable adverse event(s) will be followed until resolution or stabilization of the adverse event. For follow-up procedures see the Schedule of Events and the Assessments Section.

## **10 Study Assessments**

Every effort should be made to ensure that the protocol-required tests and procedures are completed as described. However, it is anticipated that from time to time there may be circumstances, outside of the control of the Investigator that may make it unfeasible to perform the test. In these cases, the Investigator will take all steps necessary to ensure the safety and well-being of the patient. When a protocol-required test cannot be performed, the Investigator will document the reason for this and any corrective and preventive actions that he or she has taken to ensure that normal processes are adhered to as soon as possible.

### 10.1 Physical Examinations and Vital Signs

Patients will have physical examinations to include major body systems, vital signs, assessment of Karnofsky performance status (see Appendix 1: Karnofsky Performance Status), weight and height (height will be measured at screening only) at the time points described in the Schedule of Events. If necessary, to facilitate scheduling, the physical exam may occur one day prior to study treatment.

Vital signs, including blood pressure, pulse rate, and temperature will be also recorded at the time points described in the Schedule of Events. Vital signs should be taken prior to the administration of any investigational products at the visit.

Referral to an ophthalmologist or gynecologist/urologist for organ-specific physical assessments are allowed per institutional practices.

### 10.2 Adverse Events

Adverse events experienced during trial participation will be collected per the Schedule of Events and Adverse Events Section. Each study participant will be questioned about the occurrence of adverse events in a non-leading manner. Should the treating investigator feel that the adverse event is attributed to study therapy, then dose modification guidelines in the Dose Modification Section will be followed.

### 10.3 12-Lead Electrocardiograms

All patients require a single 12-lead ECG measurement according to the Schedule of Events. The parameters to be recorded are QT, QTc, PR, and QRS. A standard 12-lead (with a 10-second rhythm strip) tracing will be used for all ECGs.

### 10.4 Laboratory Assessments

Samples for all laboratory assessments will be drawn at the time points indicated in the Schedule of Events and when clinically indicated. Laboratory tests may be performed up to 3 days prior to the scheduled clinic visit. All safety laboratory analyses will be performed by the local laboratory for each study center. All safety laboratory assessments must be reviewed by the treating investigator prior to study drug administration. When applicable, results from the pregnancy test must also be available for review prior to dosing.

**Table 8: Laboratory Assessments**

Laboratory Assessments	
CBC with Platelet Count and Differential	
 
• White Blood Cell Count
 
• Hemoglobin
 
• Platelets
 
• Absolute Neutrophil Count
 
• Absolute Lymphocytes
 

Chemistry	
 
• Complete Metabolic Panel                             
 
○ Sodium
 
○ Potassium
 
○ Chloride
 
○ Carbon Dioxide
 
 
 

	
 
○ Alkaline Phosphatase
 
○ Aspartate Aminotransferase
 
○ Alanine Aminotransferase
 
○ Urea Nitrogen
 
○ Glucose
 
○ Creatinine
 
○ Calcium
 
○ Protein
 
○ Albumin
 
○ Bilirubin
 
● Magnesium
 
● Phosphorus
 
● Lactate Dehydrogenase (LDH)
 

Coagulation	
 
● PT
 
● INR
 
● PTT
 

Quantitative Serum Immunoglobulins	
 
● Immunoglobulin A
 
● Immunoglobulin G
 
● Immunoglobulin M
 

Lipid Panel	
 
● Total cholesterol
 
● Triglycerides
 
● HDL cholesterol
 
● LDL cholesterol
 
● VLDL cholesterol
 

HIV and Hepatitis Serologies	
 
● HIV
 
● Hepatitis B surface antigen
 
● Hepatitis B surface antibody
 
● Hepatitis B core antibody
 
● HCV antibody
 
● HBV-DNA*
 
● HBC-RNA*
 

Infection Monitoring	
 
● CMV Quantitative PCR
 
● EBV Quantitative PCR
 

Graft Failure/Chimerism	
 
● Chimerism, Post-Transplant
 
● Chimerism, Post-Cell Sort, T cells
 

Pregnancy	
 
● Beta-hCG Qualitative Urine or Serum
 

\*Only required if antigen and antibody testing is positive.

### 10.5 HIV and Hepatitis Serologies

Participants with active HBV or HCV infection that requires treatment or who are at risk for HBV reactivation (i.e. positive HBsAg serology) are excluded from the study. Note: Candidates with a positive HBsAg or a negative HBsAg and positive total Hbc antibody may be included if HBV DNA is undetectable at the time of screening. Candidates positive for HCV antibody are eligible only if PCR is negative for HCV RNA. Prior test results obtained as part of standard of care before allo-HCT confirming that a participant is immune and not at risk for reactivation (i.e., hepatitis B surface antigen negative, surface antibody positive) may be used for purposes of eligibility, and tests do not need to be repeated. Participants with

positive antigen serology results must have negative PCR results. Participants whose immune status is unknown or uncertain must have results confirming immune status before enrollment.

Participants with an active HIV infection are excluded from the study. Prior HIV screening results obtained as standard of care for allo-HCT confirming an HIV-negative status may be used for determining eligibility, and tests do not need to be repeated. Participants whose HIV status is unknown must have results confirming negative status before enrollment.

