- 5.2.20 \_\_\_\_\_ Active HBV or HCV infection that requires treatment, or at risk for HBV reactivation (i.e., positive HBsAg). Participants with negative HBsAg and positive total HbC antibody may be included if HBV DNA is undetectable at the time of screening. Participants who are positive for HCV antibodies are eligible only if PCR is negative for HCV RNA. Participants whose immune status is unknown or uncertain must have results confirming immune status before enrollment. Serology results performed less than or equal to 6 months prior to the first planned dose of itacitinib are acceptable for determining eligibility.
- 5.2.21 \_\_\_\_\_ Known prior severe hypersensitivity to investigational product or any component in its formulations, including known severe hypersensitivity reactions to monoclonal antibodies (NCI CTCAE v5.0 Grade  $\geq$  3).
- 5.2.22 \_\_\_\_\_ Any condition that would, in the investigator's judgment, interfere with full participation in the study, including administration of study drug/treatment and attending required study visits; pose a significant risk to the participant; or interfere with the interpretation of study data.
- 5.2.23 \_\_\_\_\_ Unable to understand the purpose and risks of the study and to provide a signed and dated informed consent form (ICF) and authorization to use protected health information (in accordance with national and local subject privacy regulations) per the investigator's assessment.

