 Patients will be instructed to walk without assistance for 2 minutes and the distance traveled in feet will be recorded in the eCRF. This will occur at C1D1, C2D1, C3D1, C6D1, C8D1, C10D1, and EOT or PD visit.

 Adverse events will be collected for the duration of study therapy and end 30 days after the last dose of study drug. The relationship of the event to itacitinib, ECP, GVHD, and other causes (transplant, conditioning regimen, or other immunosuppressants) will be assessed as definite, probable, possible, unlikely, or not related.

 Hematology includes CBC with differential and platelets.

 Chemistry includes a LDH, magnesium, phosphorus, and a CMP (Albumin, Alkaline Phosphatase, Aspartate Aminotransferase, Alanine Aminotransferase, Total Bilirubin, Calcium, Carbon Dioxide, Creatinine, Chloride, Glucose, Total Potassium, Protein, Sodium, and Urea Nitrogen).

 Coagulation labs include PT/INR and PTT, to be collected at screening and as clinically indicated while on study.

 Lipid panel should include total cholesterol, triglycerides, HDL cholesterol, LDL cholesterol, and VLDL cholesterol. This will occur at C4D1, C7D1, C10D1, and EOT or PD visit.

 Women of child-bearing potential will require a negative pregnancy test within  $\leq$  7 days of initiating itacitinib therapy.

 HIV and hepatitis testing should include HIV, hepatitis B surface antigen, hepatitis B surface antibody, hepatitis B core antibody, HCV antibody, HBV-DNA, and HBC-RNA. HBV-DNA and HBC-RNA are only required if antigen and antibody testing is positive. Prior HIV screening results obtained as standard of care for allo-HCT confirming an HIV-negative status may be used for determining eligibility, and tests do not need to be repeated. Prior test results obtained as part of standard of care before allo-HCT confirming that a participant is immune and not at risk for reactivation (ie, hepatitis B surface antigen negative, surface antibody positive) may be used for purposes of eligibility, and tests do not need to be repeated.

 Quantitative immunoglobulins to include IgA, IgG, and IgM will be drawn C1D1, C4D1, C7D1, C10D1, EOT or PD visit.

 Absolute CD4 Count will be drawn C1D1, C4D1, C7D1, C10D1, EOT or PD visit

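### Section 10.5 conflicts with exclusion 5.2.20 on hepatitis B: its note lets HBsAg-positive candidates enter if HBV DNA is undetectable, and 5.2.20 excludes them.

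*Combined protocol and SAP*

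**What the plan says.** Exclusion 5.2.20 bars active HBV or HCV infection that needs treatment. It also bars anyone "at risk for HBV reactivation (i.e., positive HBsAg"). It then gives one route in by HBV DNA: "Participants with negative HBsAg and positive total HbC antibody may be included if HBV DNA is undetectable at the time of screening".

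Section 10.5 opens with the same exclusion, for participants "who are at risk for HBV reactivation (i.e. positive HBsAg serology) are excluded from the study". Its note follows: "Candidates with a positive HBsAg or a negative HBsAg and positive total Hbc antibody may be included if HBV DNA is undetectable". Later in the same paragraph, participants with "positive antigen serology results must have negative PCR results".

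On which text governs, Section 13 requires all Section 5 criteria to be met before registration. Section 5 is a checklist filed with the enrolling investigator's signature. Section 9.1 refers sites to the Schedule of Events and the Assessments Section, which contains 10.5, for screening procedures. Section 16.9 requires prompt reporting of exceptions to eligibility criteria.

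**The concern.** Two sections answer the same eligibility question differently, and the question is a safety one. 5.2.20 is the criterion that keeps patients at risk of hepatitis B reactivation away from a JAK1 inhibitor, which some participants will take alongside other immunosuppressants. Section 4.6 allows the lead centre and up to 3 further sites, so the conflict could be resolved differently from site to site. A patient accepted under the note would also be an eligibility exception reportable under 16.9, although the site would have been following protocol text.

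The scheduled monitoring is not built to catch such a patient early. Table 7 places hepatitis serologies at screening only. The on-study minimum in 10.6 is CMV PCR, EBV PCR and fungal monitoring, with no HBV PCR.

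**Working it through.** No arithmetic applies. The check follows one test case through each text: a candidate who is HBsAg-positive with undetectable HBV DNA.

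| Text | Answer for the test case |
|---|---|
| 5.2.20, exclusion | Ineligible: positive HBsAg is itself the stated meaning of being at risk |
| 5.2.20, HBV DNA route | Not available: limited to HBsAg-negative, core-antibody-positive patients |
| 10.5, first sentence | Ineligible, unless the note is an exception to it |
| 10.5, note | May be included |
| 10.5, antigen/PCR sentence | Treated as able to enter, given a negative PCR |

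**Does the conflict depend on how the note is parsed?** Its conditions can be grouped in two ways.

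1. Positive HBsAg; or negative HBsAg together with positive core antibody. Every HBsAg-positive candidate with undetectable DNA may enter.
2. Positive or negative HBsAg, in either case with positive core antibody. HBsAg-positive candidates who are also core-antibody-positive may enter.

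Both readings admit some patients whom 5.2.20 excludes, so the conflict does not turn on the grammar.

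**Is the note a stray phrase?** The antigen/PCR sentence suggests not. The only test named as an antigen test in Table 8 is hepatitis B surface antigen. If all HBsAg-positive patients were excluded, a PCR requirement for antigen-positive participants would have nobody to apply to.

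**Which text governs?** Section 13 names Section 5, and the checklist is the instrument for determining eligibility. On the documents, 5.2.20 prevails. But 10.5 is not marked as subordinate, and 9.1 directs sites to it during screening.

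**What would protect a patient admitted under the note?** ALT, AST and bilirubin are in the chemistry panel at treatment visits. Table 6 interrupts itacitinib for AST or ALT above 3.0 x ULN, but only where baseline values were normal. Patients with GVHD-related elevations at baseline are referred to the sponsor for discussion, and 5.1.10 admits AST/ALT up to 5 x ULN when associated with chronic GVHD. Section 10.6 asks for extra monitoring on clinical suspicion of infection. These safeguards are real but partial.

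**The case against.** The strongest reply is that the protocol already settles the matter. Section 5 is the signed checklist, Section 13 ties registration to it, and 9.1 sends sites to the Assessments Section for procedures rather than for eligibility rules. Exclusion 5.2.22 also lets the investigator refuse anyone at significant risk. All of this stands and lowers the likelihood of a wrong enrolment. It does not remove a contrary admission rule from the section that sites consult when they read the serology.

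Three stronger readings are tempting, and the documents do not support them.

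- *That 10.5 contradicts its own first sentence.* The protocol uses notes elsewhere to qualify the rule just stated (5.1.5 and 5.2.4). Read that way, 10.5 is coherent: HBsAg-positive patients are out unless HBV DNA is undetectable. The firm conflict is between 10.5 and 5.2.20, which has no such exception.
- *That footnote 17 of Table 7 fails to order the HBV DNA that 5.2.20 needs.* It says "HBV-DNA and HBC-RNA are only required if antigen and antibody testing is positive", and Table 8 repeats the condition. Read as needing both results positive, it would miss HBsAg-negative, core-antibody-positive patients. That is probably not the intent: the panel has no HCV antigen test, so HCV serology could never trigger HCV RNA. Read as any positive result, the test is ordered. This is loose wording, not a contradiction.
- *That the waiver for immune patients overrides the screening DNA rule.* It covers only results "confirming that a participant is immune and not at risk for reactivation (i.e., hepatitis B surface antigen negative, surface antibody positive"), and it waives only repeat testing. It needs no change.

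It is also fair to say that the documents do not show which text the sponsor intended. The note and the antigen/PCR sentence point one way, and 5.2.20 points the other.

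**Conclusion.** The point holds as a conflict between two sections. An eligibility rule on a safety matter is stated in 10.5 in a form that 5.2.20 forbids, and the conflict survives either parse of the note. It should be corrected.

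Its size in patients cannot be given: the documents report no hepatitis B prevalence and no expected number of HBsAg-positive candidates. The risk is limited by the precedence of Section 5, the signed checklist and the scheduled liver tests. The primary endpoint, sample size and error rates are unaffected.

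Two assumptions underlie the conclusion: that 5.2.20 expresses the intended rule, which Section 13 supports but does not prove, and that at least one site might take its hepatitis B rule from 10.5.

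**What to change.** In the note in 10.5, delete the words *a positive HBsAg or*. The note then covers only HBsAg-negative, core-antibody-positive candidates with undetectable HBV DNA, as 5.2.20 does. Delete the sentence requiring a negative PCR from antigen-positive participants. Leave 5.2.20 unchanged.

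If the sponsor did intend HBsAg-positive entry, amend 5.2.20 instead and make the exception explicit in the first sentence of 10.5. That change would widen entry on a safety criterion. Section 16.3 sends amendments that increase risk to the DSMC for review and to the PRMC and IRB for approval.

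Optional tidy-up in footnote 17 and Table 8, where the trigger is "Only required if antigen and antibody testing is positive": require HBV DNA if HBsAg is negative and total core antibody is positive, and HCV RNA if HCV antibody is positive. Correct *HBC-RNA* to *HCV-RNA*, the term used in 5.2.20 and 10.5.

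The cost is a wording amendment. No patient eligible under Section 5 is lost. The tidy-up adds no test beyond what 5.2.20 and 10.5 already need to settle eligibility.
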